While treatment with thrombolytics is standard of care for patients arriving within 0 to 4.5 hours, thrombolytics have not been shown to benefit patients who present beyond this time window (Emberson et al. 2014). Consequently, only a few patients in the recently completed late-window endovascular trials (DEFUSE 3 and DAWN) received *IV* thrombolytics.

A small study (TIAS; Kate et al. 2018) suggested the feasibility of treating patients far outside of established treatment windows with a novel thromolytic agent (tenecteplase 0.25 mg/kg). Results showed that 9/16 patients (56.3%) had an improvement in NIHSS score by ≥ 4 points at 24 hours. The sICH rate was 6.3% (n=1). The median mRS score at 90 days was lower in the tenecteplase group (2 [range: 2–2.5]) than in the untreated mismatch (3 [range: 3–4]; *odds ratio [OR]* 2.4; 95% CI 1.1–5.3; *p*=0.03) and non-mismatch (5 [range: 4–6]; *OR* 4.5; 95% CI 1.6–12.8; *p*=0.005) patients. The proportion of patients with mRS 0–2 was significantly higher in the tenecteplase group (73.3%) than in the untreated mismatch (22.2%) and non-mismatch (4.3%, *p*<0.001) groups. There were no deaths in the tenecteplase-treated and untreated mismatch groups.

Whether this “bridging” thrombolysis approach is beneficial compared with thrombectomy alone, when neurointervention is immediately available, has been questioned and is now the subject of randomized trials. However, for many institutions, thrombectomy involves transfer to an external hospital. There are also situations in which a planned thrombectomy is delayed or the neuro-interventionist is either unable to gain access to the cerebral circulation or unable to completely remove the thrombus. Improved *IV* thrombolysis options may increase the proportion of patients with early reperfusion prior to thrombectomy. This would have substantial clinical benefits and likely improve patient outcomes, and may reduce costs given the strong relationship between time to reperfusion and disability as well as potential reductions in the requirement for resource-intensive thrombectomy.

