6.4.3 Exploratory Analyses

The mRS score at Day 90 will be analyzed in the following subgroups:

- Occlusion type (ICA/M1 or M2 occlusions)
- Randomization site (ECC or nECC)
- Proportion of patients where planned thrombectomy was not performed (including patients with partial or complete recanalization of the qualifying vessel occlusion which includes patients who did not go to angiography suite because non-invasive imaging demonstrated recanalization, or patients who have undergone catheter angiography and are found to no longer to have an occlusion of the qualifying vessel)
- *Overall survival at Day 90*

For each of the above-mentioned subgroups, the distribution of the mRS scores will be compared between the treatment groups by a proportional odds model controlling for the randomization strata and baseline mechanical thrombectomy planned status, as appropriate.

For patients who are randomized at an nECC and transferred to an ECC for endovascular therapy, the proportion of patients where planned thrombectomy was not performed will be compared between treatment groups using a logistic regression model adjusted by baseline age group and baseline NIHSS.

For the following continuous exploratory endpoints, treatment groups will be compared using the van Elteren's test, adjusting for the randomization stratification factors *and baseline mechanical thrombectomy planned*:

- Median final infarct volumes at *the 72–96 hour visit* or discharge (if patient is being discharged prior to *the 72–96 hour visit*); and
- Median infarct growth at *the 72–96 hour visit* or discharge (if patient is being discharged prior to *the 72–96 hour visit*).

The appropriate scoring algorithm will be employed to score the Neuro-QoL responses and scores will be compared between the treatment groups. Details of the exploratory analyses will be provided in the SAP.

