2.2.3 Exploratory Efficacy Endpoints

The following exploratory efficacy endpoints will be analyzed:

- Median final infarct volumes at 72-96 hours visit or discharge (if patient is being discharged prior to 72-96 hours visit).
- Median infarct growth at 72-96 hours visit or discharge (if patient is being discharged prior to 72-96 hours visit).
- Ordinal mRS score at Day 90 by occlusion type (M1/ICA or M2 occlusions).
- Ordinal mRS score at Day 30 and Day 90 by randomization site (ECC or nECC).
- Proportion of patients who are randomized at an nECC and transferred to an ECC for endovascular therapy for whom planned thrombectomy was not performed.
- Proportion of patients readmitted within 30 days from discharge.
- Proportion of patients requiring one pass with endovascular therapy device (endovascular patients only).
- Mean Quality of Life in Neurological Disorders (Neuro-QoL) scores by domain.
- Proportion of patients where planned thrombectomy was not performed.
- Overall survival at Day 90.

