4.6 EFFICACY ANALYSIS

Efficacy analyses will be performed using the ITT population with patients grouped according to treatment assigned at randomization. Available data regardless of adherence to the protocol will be included in the efficacy analyses; this includes data from patients who discontinued prematurely from the study.

Deviation from the AHA/ASA treatment guidelines for standard of care (i.e. mechanical thrombectomy [MT] is planned for the patient but not performed due to various reasons) is considered an intercurrent event in this study. COVID-19 infections are considered another type of intercurrent event. COVID-19 infections during the follow-up period will be captured as AEs. In efficacy analyses, treatment policy strategy will be applied to both COVID-19 and non-COVID-19 intercurrent events. That is, all collected data will be used regardless of the occurrence of these intercurrent events.

Visit windows will be derived according to [Table 2](#) and applied for all clinical efficacy assessments. If there are multiple assessments within the same window, the one closest to the target time point will be used. Assessments that are outside of the defined windows will not be used in analysis, except they may provide a value for the last observation carried forward (LOCF) imputation in the case of mRS (see Section [4.9.1.1](#)).

Table 2 Definition of Visit Windows

Visit	Target Time	Window: mRS, GOS, BI, Neuro-QoL*	Window: NIHSS	Window: imaging
24 hours	24 hours	N/A	18 to 30 hours	18 to 30 hours
72-96 hours	84 hours	N/A	60 to 96 hours	60 to 120 hours
Day 5	5 days	4 to 6 days	5 to 6 days	N/A
Day 30	30 days	15 to 60 days	15 to 60 days	N/A
Day 90	90 days	61 to 120 days	61 to 120 days	N/A

BI = Barthel Index; GOS = Glasgow Outcome Scale; mRS = modified Rankin Scale; Neuro-QoL = Quality of Life in Neurological Disorders; NIHSS = National Institutes of Health Stroke Scale.

* Assessed only at Day 90 Visit

All analyses of efficacy endpoints (primary, secondary, and exploratory) will be evaluated for superiority. Analyses will be adjusted for all or a subset of the following variables:

- Age (≤ 70 vs. > 70 years of age)
- Type of occlusion (ICA/M1 vs. M2)
- Baseline NIHSS (≤ 15 vs. > 15)
- Randomization site (ECC vs. nECC)
- Mechanical thrombectomy planned (Yes vs. No)
- Protocol version (Protocol V1-4 vs Protocol V5).

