4.6.3.3 Planned Thrombectomy Not Performed for nECC to ECC Transfers

Some patients who were randomized at an nECC may be transferred to an ECC for endovascular therapy. Occasionally, a planned thrombectomy may not need to be performed on such patient, for example, if symptom improvement was observed prior to the planned thrombectomy. This improvement could occur before, during, or after the transfer of the patient.

The proportion of patients where a planned thrombectomy was not performed for patients randomized at an nECC and transferred to an ECC for endovascular therapy will be summarized by treatment group and analyzed using logistic regression. The model will be adjusted as specified in Section 4.6 but excluding the planned thrombectomy variable. Observed counts and percentages for tenecteplase and placebo arms, and model based odds ratio, corresponding Wald 95% CI and p-value will be produced.

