4.6.3.7 Planned Thrombectomy Not Performed

A planned thrombectomy may not be performed in some cases. This includes patients with partial or complete recanalization of the qualifying vessel occlusion who did not go to angiography suite because non-invasive imaging demonstrated recanalization, or patients who have undergone catheter angiography and are found to no longer to have an occlusion of the qualifying vessel.

The proportion of patients where a planned thrombectomy was not performed due to partial or complete recanalization will be summarized by treatment group and analyzed using logistic regression adjusted as specified in Section 4.6 but excluding the planned thrombectomy variable. Observed counts and percentages for tenecteplase and placebo arms, and model based odds ratio, corresponding Wald 95% CI and p-value will be produced.

4.6.3.8 Overall Survival at Day 90

Cumulative incidence of all deaths will be presented by means of Kaplan-Meier plots if there are sufficient events (at least 5 in each treatment group). Time to death since randomization will be analyzed with a stratified log-rank test using variables as specified in Section 4.6. Death occurred up to Day 90 visit (or within 120 days since randomization, which is the study day cut-off for efficacy outcome evaluation) will be included in the analysis. Patients who did not die up to Day 90 visit will be censored at the last study assessment date. In addition, death occurred after Day 90 visit and the relatedness of death is determined by having a related fatal AE will also be included in the analysis.

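### The nECC-to-ECC endpoint in SAP 4.6.3.3 counts a planned thrombectomy not performed for any reason, so its odds ratio cannot be read as thrombectomy avoided

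*SAP*

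**What the plan says.** SAP 4.6.3.3 opens with the reason for the endpoint: "a planned thrombectomy may not need to be performed on such patient, for example, if symptom improvement was observed" before the procedure. It then defines what is analysed: "The proportion of patients where a planned thrombectomy was not performed for patients randomized at an nECC and transferred to an ECC". This is summarized by arm and compared by adjusted logistic regression, with an odds ratio, Wald 95% CI and p-value. No reason for non-performance enters the definition.

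The other places that describe this endpoint add no condition. The list in SAP 2.2.3 reads "transferred to an ECC for endovascular therapy for whom planned thrombectomy was not performed", and Protocol 6.4.3 says that "the proportion of patients where planned thrombectomy was not performed will be compared between treatment groups using a logistic regression model".

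The all-patient version in SAP 4.6.3.7 is narrower: "The proportion of patients where a planned thrombectomy was not performed due to partial or complete recanalization".

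The documents recognise that reasons differ. SAP 4.6 describes an intercurrent event in which thrombectomy "is planned for the patient but not performed due to various reasons". Protocol 1.3 mentions situations in which "the neuro-interventionist is either unable to gain access to the cerebral circulation".

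**The concern.** The section motivates the endpoint by one kind of event, a procedure made unnecessary, and analyses a larger set. A transferred patient whose thrombectomy is cancelled for a reason other than recanalization is an event under 4.6.3.3 and a non-event under 4.6.3.7. The two endpoints have nearly the same name, and the SAP does not explain the difference.

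SAP 4.6 evaluates every efficacy endpoint, exploratory ones included, for superiority. A reader shown an odds ratio above 1 here will take it to mean that tenecteplase spared transferred patients a thrombectomy. Because the event mixes lysis with failure and harm, the odds ratio has no fixed direction. Bleeding is the main complication the Protocol names for the drug (5.1.1.1), so cancellations for harm need not be balanced between arms.

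**Working it through.** **Which reasons count, from the text**

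| Place | Event | Condition on reason |
|---|---|---|
| SAP 2.2.3 (transfers) | planned thrombectomy not performed | none |
| Protocol 6.4.3 (transfers) | same | none |
| SAP 4.6.3.3 (transfers) | same | none; symptom improvement is only an example in the introduction |
| SAP 4.6.3.7 (all patients) | same | partial or complete recanalization |

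- *Failed access.* SAP 4.6.3.3 does not define performance. SAP 4.6.3.5 treats a thrombectomy as performed when the clot could be reached, and SAP 4.6.5 when it was successfully manipulated. On either reading a failed-access case is not performed, and so is an event.
- *Haemorrhage, deterioration, death.* SAP 4.6.3.3 names none of these. They count because nothing excludes them.
- *Denominator.* Only patients actually transferred for endovascular therapy are included. Harm that prevents the transfer removes the patient from the analysis. Harm during or after the transfer makes the patient an event.

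**Illustration of size**

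The documents give no number of transfers, no cancellation rate and no power for this endpoint, so there is no figure to reproduce and every rate below is an assumption. For event rates a (tenecteplase) and b (placebo), OR = [a/(1−a)] / [b/(1−b)].

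*A. Equal lysis, more harm-related cancellations on tenecteplase.* The recanalization-only OR is 1.00 in every row. The upper harm rate, 6.5%, is borrowed from the symptomatic haemorrhage rate of 2/31 in one dose-ranging study (Protocol 3.3.1). It is a haemorrhage rate, not a cancellation rate.

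| Lysis, both arms | Harm, tenecteplase vs placebo | All-reason rates | All-reason OR |
|---|---|---|---|
| 5% | 4% vs 2% | 9% vs 7% | 1.31 |
| 5% | 6.5% vs 2% | 11.5% vs 7% | 1.73 |
| 10% | 4% vs 2% | 14% vs 12% | 1.19 |
| 10% | 6.5% vs 2% | 16.5% vs 12% | 1.45 |
| 20% | 4% vs 2% | 24% vs 22% | 1.12 |
| 20% | 6.5% vs 2% | 26.5% vs 22% | 1.28 |

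For example, (0.14/0.86) / (0.12/0.88) = 1.19. With harm equal at 2% in both arms the all-reason OR is 1.00. With the harm rates swapped, 2% vs 4%, it is 1/1.19 = 0.84.

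*B. A real lysis difference plus equal non-lysis cancellations.* Lysis of 22% vs 10% is borrowed from Protocol Table 2, the rates of reperfusion or no retrievable thrombus at first angiography. That trial compared tenecteplase with alteplase within 4.5 hours, so the figures only set a scale.

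| Non-lysis cancellations per arm | All-reason rates | OR |
|---|---|---|
| 0% | 22% vs 10% | 2.54 |
| 5% | 27% vs 15% | 2.10 |
| 10% | 32% vs 20% | 1.88 |
| 20% | 42% vs 30% | 1.69 |

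**The case against.** **It is exploratory.** The endpoint is not in SAP Table 3, carries no alpha and triggers no stopping rule. This stands. A reader might infer that the definition threatens the type I error rate or a claim of the trial; the documents do not support that.

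**The two endpoints may be meant to differ.** An all-reason count in transfers and a reason-specific count in all patients are listed separately. An all-reason count also avoids judging reasons after randomization, and neither section calls non-performance a success. That supports keeping the all-reason figure as a description. It does not support testing it for superiority under an introduction about procedures no longer needed.

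**Treatment policy already covers it.** SAP 4.6 applies that strategy when a planned thrombectomy is not done, meaning that outcome data are used regardless. Here non-performance is itself the outcome, so the strategy does not settle which cases belong in the event.

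**Harm is reported elsewhere.** Symptomatic haemorrhage and mortality are presented by arm (SAP 4.8.2.1 and 4.8.2.3), so harm is not hidden. Those tables still do not show how much of this odds ratio comes from harm.

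**The harm share may be small.** The interval between transfer and angiography is short, and Protocol Table 2 gives 1% symptomatic haemorrhage over 36 hours. Nothing in the documents suggests that access failure differs by arm, so on its own it would dilute the odds ratio and not reverse it. Both points stand, and they are why the sizes above are illustrations only.

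**Conclusion.** The point holds as one of definition and interpretation. As written, SAP 4.6.3.3 gives an odds ratio and p-value for an event that mixes lysis with failed access and with harm during or after transfer, while SAP 4.6.3.7 isolates recanalization. Under the assumed rates, the all-reason odds ratio is about 1.1 to 1.7 when lysis is equal and harm-related cancellations are more frequent on tenecteplase. A lysis odds ratio of 2.54 falls to about 2.1 to 1.7 when equal non-lysis cancellations are added. These ranges rest on chosen rates and do not predict this trial's result.

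Three stronger readings are not supported:

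- A reader might infer that the endpoint is biased towards tenecteplase. The direction depends on cancellation rates that the documents do not give.
- A reader might infer that every haemorrhage, decline or death that stops thrombectomy counts as an event. Those that prevent the transfer fall outside the denominator.
- A reader might infer that avoiding thrombectomy is the stated rationale for treating at non-endovascular centres. Protocol 1.1 speaks of a reduced need for transfer. Protocol 1.3 puts early reperfusion and outcome first and mentions less thrombectomy as a potential cost saving.

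**What to change.** In SAP 4.6.3.3:

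- Define the analysed event as in 4.6.3.7: planned thrombectomy not carried out because the qualifying vessel had partly or completely recanalized.
- Count all other transferred patients as non-events.
- Keep the all-reason proportion as a descriptive summary by arm, with the reasons where they were recorded.
- Add symptom improvement to the event only if it was recorded as a reason for non-performance. If it was not, the introductory example should be reworded, because a patient who improved without shown recanalization would be a non-event.
- State that the analysed event is narrower than the wording in SAP 2.2.3 and Protocol 6.4.3.

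The cost is a short wording change, fewer events in an already small exploratory analysis, and reliance on the recorded reason. SAP 4.6.3.7 already requires that reason for recanalization. The case report form is not among the documents, so they do not show whether haemorrhage, deterioration, access failure or symptom improvement were captured as reasons. The tabulation should be limited to what was collected.

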1. BACKGROUND

1.1 **BACKGROUND ON ACUTE ISCHEMIC STROKE**

Acute ischemic stroke (AIS) is the fifth leading cause of death in the U.S. Approximately 795,000 people suffer a stroke annually, with 23% due to recurrent stroke. Projections estimate that by the year 2030 an additional 3.4 million U.S. adults 18 years and older, representing 3.88% of the adult population, will experience a stroke, which is a 20.5% increase in prevalence from 2012 (Ovbiagele et al. 2013). Stroke is also the leading cause of serious, long-term disability. Approximately 2% of females and 3% of males are disabled from stroke (CDC 2017). From 2013 to 2014, the direct and indirect costs of stroke in the U.S. totaled \$40.1 billion. It is projected that total direct medical costs will more than double, from \$36.7 billion to \$94.3 billion, between 2015 and 2035 (Benjamin et al. 2018).

Intravenous thrombolysis with alteplase remains the standard of care prior to thrombectomy for eligible patients within 4.5 hours of ischemic stroke onset (AHA/ASA 2018). However, alteplase succeeds in reperfusing large vessel arterial occlusion prior to thrombectomy in only a minority of patients (Campbell et al. 2018). Results of previous non-randomized studies have suggested that patients who have a mismatch between the volume of brain tissue that may be salvaged and the volume of infarcted tissue as seen on imaging could benefit from reperfusion of occluded proximal anterior circulation vessels, even when the reperfusion is performed more than 6 hours after the patient was last known to be well (Jovin T et al. 2011; Lansberg et al. 2015). Treatment benefit is strongly dependent on time-to-reperfusion and, as many patients have treatment delays due to inter-hospital transfers (or in some cases difficult vascular access), improved approaches to intravenous thrombolysis that decrease the need for transfer could substantially improve patient outcomes.

1.2 **BACKGROUND ON TENECTEPLASE**

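### The nECC-to-ECC thrombectomy endpoint is analysed only in patients who were transferred, a post-randomization condition that study drug may affect

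*SAP*

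**What the plan says.** SAP 2.2.3 lists the endpoint as "Proportion of patients who are randomized at an nECC and transferred to an ECC for endovascular therapy for whom planned thrombectomy was not performed". The analysis sentence in SAP 4.6.3.3 keeps the condition: "The proportion of patients where a planned thrombectomy was not performed for patients randomized at an nECC and transferred to an ECC" for endovascular therapy is summarized by arm and compared by logistic regression with a model-based odds ratio. Protocol 6.4.3 opens its version with "For patients who are randomized at an nECC and transferred to an ECC for endovascular therapy", and the Protocol synopsis and Table 3 agree.

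SAP 4.6.3.3 does not treat transfer as certain: "Some patients who were randomized at an nECC may be transferred to an ECC for endovascular therapy". It gives symptom improvement as an example of why the procedure may not be needed, and adds: "This improvement could occur before, during, or after the transfer of the patient".

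The neighbouring endpoint in SAP 4.6.3.7 has no transfer condition but is limited by reason: "The proportion of patients where a planned thrombectomy was not performed due to partial or complete recanalization". SAP 4.1.1 bases all efficacy analyses on the ITT population.

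**The concern.** Being randomized at an nECC is a baseline fact, so restricting to those patients preserves the randomized comparison. Being transferred comes after randomization, and the trial's own rationale allows that treatment may change it. Protocol section 1.1 says that "improved approaches to intravenous thrombolysis that decrease the need for transfer could substantially improve patient outcomes".

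A patient with planned thrombectomy who stays at the nECC has, in substance, had a planned thrombectomy not performed, yet falls outside the analysis set. Neither document says how to count such a patient. The transferred patients in the two arms may then differ in ways that randomization does not control. At stake is the interpretation of one exploratory result that bears directly on whether the drug reduces the need for transfer and thrombectomy.

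**Working it through.** The documents give no rate, sample size or power for this endpoint, so there is no plan figure to reproduce. The definitional point rests on the texts set out above. The size can only be illustrated.

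**Inputs (all assumed).**
- p = proportion of nECC-randomized, thrombectomy-planned patients whose thrombectomy is not performed.
- c = share of those patients who are never transferred.
- All other patients are transferred. No thrombectomy is done without transfer.
- T = tenecteplase, P = placebo.

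**Formulas.** Cancelled transfers remove pc from both numerator and denominator:
- proportion seen among transferred = p(1-c)/(1-pc)
- odds seen = p(1-c)/(1-p) = (1-c) × true odds
- OR seen = true OR × (1-cT)/(1-cP)

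**Main case: pT = 30%, pP = 15%.** True OR = (0.30/0.70)/(0.15/0.85) = 2.43; true difference 15.0 points.

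| cT | cP | Seen, T vs P | Difference (points) | OR seen |
|---|---|---|---|---|
| 0% | 0% | 30.0% vs 15.0% | 15.0 | 2.43 |
| 25% | 25% | 24.3% vs 11.7% | 12.6 | 2.43 |
| 50% | 50% | 17.6% vs 8.1% | 9.5 | 2.43 |
| 50% | 25% | 17.6% vs 11.7% | 6.0 | 1.62 |
| 50% | 0% | 17.6% vs 15.0% | 2.6 | 1.21 |
| 75% | 25% | 9.7% vs 11.7% | -2.0 | 0.81 |

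Example for 50% vs 25%: T = 0.30 × 0.50/(1 - 0.15) = 0.176; P = 0.15 × 0.75/(1 - 0.0375) = 0.117; OR = 2.43 × 0.50/0.75 = 1.62.

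The factor works in both directions. With cT = 25% and cP = 50%, the OR seen would be 2.43 × 0.75/0.50 = 3.64, an overstatement.

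**Smaller proportions: 20% vs 10%.** The true OR is 2.25. It stays 2.25 at equal shares, and becomes 1.50 (50% vs 25%), 1.13 (50% vs 0%) or 0.75 (75% vs 25%).

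**Precision.** Assume 50 such patients per arm, 30% vs 15%, two-sided 0.05. Power is 0.43 with everyone in the denominator, 0.36 with 25% cancelled in both arms, and 0.27 with 50% cancelled in both. Equal cancellation leaves the odds ratio intact but still costs information.

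**The case against.** The strongest reply has four parts.

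1. **SAP 4.6.3.7 already counts some of these patients.** It has no transfer condition and includes patients who never reached the angiography suite because imaging showed recanalization. This stands in part. But that endpoint pools all sites, and its examples rest on imaging or angiography. A transfer cancelled on symptom improvement alone is not clearly counted in either place.

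2. **The SAP need not contradict itself.** Improvement before transfer can describe a patient who improved and was still transferred, and that patient is kept. This is a fair reading. It does not help the patient who was never transferred.

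3. **Counting all reasons is defensible.** SAP 4.6 treats a planned but unperformed thrombectomy, whatever the reason, as an intercurrent event under a treatment policy strategy. An all-reason endpoint beside a recanalization-only one is a sensible pair. This stands, and the missing piece is a table of reasons. Limiting the event to recanalization would do harm, because a patient who improved clinically without repeat vessel imaging would become a non-event. Suppose thrombectomy is avoided before transfer in 10% vs 3% and after transfer in 10% vs 4%. If none of the former had imaging, that rule would give 10% vs 4% (OR 2.7), against 11.1% vs 4.1% (OR 2.9) under the present definition.

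4. **The consequence is small.** The endpoint is exploratory and absent from the testing order in SAP Table 3, and these patients remain in the ITT primary analysis. This stands.

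A reader might go further and infer that the definition drops successes mainly on tenecteplase and so understates its effect. The documents do not support that. They report no cancellation rate in either arm, and transfers cancelled for haemorrhage or deterioration also leave the denominator.

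**Conclusion.** The definition conditions on a post-randomization event that treatment may influence, and cancelled transfers have no stated place in it. That follows from the text alone.

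The size and direction of the bias are unknown. The odds ratio is unaffected if the never-transferred share of unperformed thrombectomies is equal across arms, shrinks by (1-cT)/(1-cP) if the share is larger on tenecteplase, and grows if it is larger on placebo. All numerical results rest on assumed rates.

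It would be tempting to say that a large part of the effect is lost. On the rates in part 3 of the objection, the difference does fall from 13 points (20% vs 7%) to 7 points (11.1% vs 4.1%), but the odds ratio, which is what the SAP reports, moves only from 3.3 to 2.9. The rates are invented, so neither figure can serve as an estimate for this trial.

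The issue is minor. It touches one exploratory endpoint and leaves the primary analysis and type I error control as they are.

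**What to change.** In SAP 4.6.3.3:

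- **Denominator:** all ITT patients randomized at an nECC with mechanical thrombectomy planned at baseline, transferred or not. Planned status is already an adjustment variable in SAP 4.6 and a subgroup in SAP 4.6.5.
- **Event:** any planned thrombectomy not performed, including cancelled transfers.
- **Reasons:** tabulate events by arm as recanalization, symptom improvement, haemorrhage or deterioration, and other. Show the number transferred in each arm.
- **Supportive analysis:** keep the transferred-only comparison, since it is the Protocol's wording.

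The model can stay as it is. SAP 4.6.3.3 already leaves out the planned-thrombectomy variable, which is constant in this denominator.

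The cost is a short SAP revision and a note that the main definition departs slightly from the Protocol. The documents do not show that reasons for a cancelled transfer are recorded as such, so the reasons table may be incomplete. An unknown category should be allowed for.
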